Questionnaires: Known categorical variables that are affecting fetal growth are smoking, alcohol, diabetes, baby gender, ethnic origin and parity. Known continuous variables are birth weight, gestational length, maternal height and weight²⁴. The country of origin will provide the ethnic origin more precisely. Medical conditions and concomitant medication of the mother are documented. Relevant laboratory parameters - if available from the clinical routine - will be added to the dataset: Hemoglobin, Eosinophils, HIV-status and Hepatitis B and C status (Hbs-Ag, Anti-HCV). Factors resulting from exposition that can influence serological results are: previous history of Bilharzia, previous treatment and time since previous treatment of Bilharzia, fresh water contacts in the area of origin or on the way to Europe, time since migration to Europe and the type of travel to Europe. Data will be collected with a standardized case report form (eCRF) and will be pseudonymised at source. Property transfer for material (placenta and serum) is part of the questionnaire.

Sample size estimates: We estimated that n=200 mother-newborn pairs can be realistically ascertained within the funding period in the participating study centers in Germany, Italy and Ireland. Furthermore,

we expect 20% of the serologic tested samples to be positive (i.e. $n_{\text{positive}} \approx 40$; $n_{\text{negative}} \approx 160$ based on previous literature¹³⁻¹⁵). Intrauterine growth restriction (IUGR) is defined by birth weight below the 10th percentile of the reference curves. It occurs in 5-10% of all pregnancies and can be compared across multi-ethnic populations^{16,18-20}. We hypothesize that serologic positivity will result in reduced birth weight. In the given setting of our project, a study with $n=200$ mother-newborn pairs has a power of 80% to detect a standardized mean difference in birth weight percentiles of 0.5 (in units of standard deviations of a standard normal distribution; a moderate effect according to Cohen) at a significance level $\alpha=5\%$ (two-sided; planning by Student's test for 4:1 sample size ratio; nQuery 3.0).

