Statistical analysis: The primary analysis will be a Mann-Whitney-Wilcoxon test to compare birth weight percentile distributions between the two groups of newborns born to seronegative and seropositive mothers (at a two-sided significance level $\alpha=5\%$). We will also evaluate known factors that influence birth weight (see above in paragraph questionnaire) in univariate regression models for the birth weight percentile outcome. Single confounders with a potential impact on the relationship between serum-status and birth weight percentile will be included in multiple linear regression models based on the univariate results ($p<0.2$). Similar to these sensitivity analyses, all other inferential statistics to compare the secondary outcomes between the two groups of negative and serum-positive newborns will be done exploratively using Fishers exact tests for the dichotomous variables (IUGR, stillbirth and premature delivery) while reporting the respective effects size estimates and 95% confidence intervals.

References

1. Richter J RA. Schistosomiasis oder Bilharziose. In: Löscher T. BGD, ed. Tropenmedizin in Klinik und Praxis. 4 ed. Stuttgart & New York 2010:676-703.
5. Bittencourt AL, Cardoso de Almeida MA, Lunes MA, Casulari da Motta LD. Placental involvement in schistosomiasis mansoni. Report of four cases. The American journal of tropical medicine and hygiene 1980;29:571-5.
7. Olds GR. Administration of praziquantel to pregnant and lactating women. Acta Trop 2003;86:185-95.
9. Siza JE. Risk factors associated with low birth weight of neonates among pregnant women attending a referral hospital in northern Tanzania. Tanzania journal of health research 2008;10:1-8.

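### The p<0.2 univariate screen for adjustment covariates can leave the adjusted serology estimate biased towards zero; the adjustment set should be named in advance

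*Combined protocol and SAP*

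**What the plan says.** The Statistical analysis section sets out three steps.

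- The primary analysis is an unadjusted Mann-Whitney-Wilcoxon comparison of birth weight percentiles by maternal serostatus.
- Next, "We will also evaluate known factors that influence birth weight (see above in paragraph questionnaire) in univariate regression models", with birth weight percentile as the outcome.
- Finally, "Single confounders with a potential impact on the relationship between serum-status and birth weight percentile" are the variables that "will be included in multiple linear regression models based on the univariate results", with p<0.2 as the threshold. The section then refers to these models as sensitivity analyses.

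No variable is forced into the multiple regression. The words about a potential impact on the serology-outcome relationship suggest a second consideration, but no criterion for it is given.

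The candidates come from the Questionnaires section: "Known categorical variables that are affecting fetal growth are smoking, alcohol, diabetes, baby gender, ethnic origin and parity" and "Known continuous variables are birth weight, gestational length, maternal height and weight". It adds that "The country of origin will provide the ethnic origin more precisely". The candidate list is therefore fixed in advance, but the final adjustment set is not.

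**The concern.** The plan takes variables it already regards as established determinants of fetal growth, re-tests each in about 200 pairs, and adjusts only for those that pass. The screen measures the association of covariate and outcome without serostatus in the model. Suppose infection lowers the percentile, as the study hypothesises, and a covariate is more favourable among seropositive women. The two influences then partly cancel in the univariate regression, the covariate looks unrelated to the outcome, and it is left out. That is the confounder whose omission hides a true deficit.

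The primary test makes no adjustment, so these regressions are the only place where confounding is addressed. A reader deciding whether an association, or its absence, is credible must rely on them.

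**Working it through.** **Inputs from the document (Sample size estimates; Statistical analysis).** About 40 seropositive and 160 seronegative pairs, standardised difference 0.5, two-sided alpha 5%, entry threshold p<0.2.

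**The plan's own figure.** Noncentrality = 0.5 × √(40 × 160 / 200) = 0.5 × √32 = 2.83. Normal approximation: Φ(2.83 − 1.96) = 80.7%. Noncentral t with 198 df: 80.4%. The stated 80% reproduces.

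**Chance that a real determinant passes.** By Fisher's z with n = 200, a covariate with true correlation r passes with probability Φ(m − 1.28) + Φ(−m − 1.28), where m = atanh(r) × √197. For r = 0.10, m = 1.41 and the probability is 55%. For r = 0.05 it is 30%, and for r = 0.15 it is 80%.

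**Why masking confounders are dropped more often.** Let g be the covariate's effect (SD per SD), d its imbalance between serogroups in SD, β = −0.5 the serology effect and π = 0.2 the share seropositive. The univariate slope that the screen sees is g + β π(1 − π)d / [1 + π(1 − π)d²]. With d = 0.8 the second term is −0.5 × 0.128 / 1.102 = −0.058.

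- Masking (g = +0.10): 0.10 − 0.058 = 0.042.
- Exaggerating (g = −0.10): −0.10 − 0.058 = −0.158.

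The standard error of this slope is about 0.069, so z is about 0.6 and 2.3. The cut-off is 1.28, which implies dropping about 72% and 15% of the time. Simulation gives the same 72% v 15%; at d = 0.5 it gives 64% v 26%, and at d = 1.2, 77% v 7%. Strong confounders (slope 0.3) are kept at least 98.8% of the time.

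**Consequence for the serology estimate.** The documents give no confounder strengths, so all of these are assumptions. Each setting uses 3,000 or more simulated studies, residual SD 1, the percentile treated as a normal score, true effect −0.5 SD, and slope 0.10 unless stated. Crude bias is roughly the sum of slope × imbalance, for example 8 × 0.10 × 0.4 = 0.32.

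| Confounders | Crude bias | Screened: bias / coverage / power | Full-set power |
|---|---|---|---|
| One masking, binary (effect −0.3; 30% of seronegative v 5% of seropositive) | +0.08 | +0.03 / 94.4% / 75% | 78% |
| One masking, imbalance 1.2 | +0.12 | +0.08 / 92.5% / 64% | 72% |
| Four masking, imbalance 0.8 | +0.32 | +0.12 / 90.0% / 49.5% | 64.0% |
| Six masking, imbalance 0.4 | +0.24 | +0.08 / 93.7% / not tabulated | not tabulated |
| Eight masking, imbalance 0.4 | +0.33 | +0.10 / 91.4% / 56% | 70% |
| Three masking and three exaggerating, imbalance 0.4 | 0 | +0.04 / 94.4% / 68% | 73% |
| Eight exaggerating, imbalance 0.4 | −0.32 | −0.01 / 95.0% / 74% | 71% |

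Across the four-masking settings, bias ran from +0.05 to +0.12 SD and coverage from 90.0% to 94.1%. With two masking and two exaggerating confounders, bias ran from +0.04 to +0.10 SD and coverage from 91.1% to 94.4%, the worse ends at larger imbalances. With no true effect, screened bias was about +0.02 to +0.04 SD at most, coverage 94.4-95.6% and type I error 4.4-5.6%. The full set kept bias within about 0.01 SD and coverage at 94-96%.

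**The case against.** The strongest reply has four parts.

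1. **These are sensitivity analyses.** This is correct: the screen cannot change the primary test or its type I error. It does not remove the point, because nothing else in the plan adjusts for confounding.

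2. **The harm is conditional.** This also stands. A reader might infer that the rule necessarily biases the estimate and makes the intervals too short, or that chance alone decides the covariate set. The documents support neither. They give no confounder strengths and no imbalance by serostatus, and strong confounders are almost always kept. The eight-masking setting exceeds what the plan lists: of ten named variables (six categorical, four continuous), removing birth weight, sex and gestational length leaves seven.

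3. **Screening is better than no adjustment.** This is true when confounding runs in one direction. In the eight-masking setting it removes about two thirds of the crude bias (from 0.33 to 0.10 SD). It is not true when opposing confounders balance: the crude estimate is then nearly unbiased, while the screened one is shifted by 0.04 SD or more because mainly the exaggerating confounders are retained. The direction is not known in advance.

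4. **The wording allows subject-matter judgement.** The phrase about a potential impact on the relationship points that way, but p<0.2 is the only operational criterion.

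**Conclusion.** The point holds as a conditional weakness in the adjusted sensitivity analyses. The entry rule tends to omit weak-to-moderate masking confounders and can pull the adjusted serology estimate towards zero.

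For an effect of −0.5 SD, the size is about 0.03 SD with one masking confounder (0.08 SD at an imbalance of 1.2 SD). It is about 0.04 SD with mixed directions (up to 0.10 SD at larger imbalances) and mostly 0.08 to 0.12 SD with four to eight masking confounders. The upper value is 0.12 / 0.5 = 24% of the effect. Coverage is 90-94% with several masking confounders and otherwise close to 95% unless imbalances are large. Power is about 5 to 15 points below the full model when several masking or mixed-direction confounders are present (73 − 68 = 5; 64.0 − 49.5 = 14.5). With exaggerating confounders only, or no true effect, the harm is negligible.

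All these sizes rest on assumed strengths and imbalances. It would be wrong to conclude that the primary result is compromised or that the adjusted estimate is certain to be biased. The change is worth making because a better rule is available from data already collected.

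**What to change.** Delete the p<0.2 entry rule and name the adjustment set before data lock, on subject-matter grounds, from the Questionnaires list.

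- **Include**, for example: smoking, alcohol, parity, maternal height and weight, and ethnic or country origin grouped into a few regions. Include diabetes too, unless such women are excluded under the criterion on conditions that affect fetal growth. The plan should say which applies.
- **Leave out** birth weight, which is the outcome, and sex and gestational length. The Assessments paragraph lists the last two among the values needed to derive the outcomes, so the percentile appears to use them already.
- **Fit** one model with serostatus and the whole set, whatever the p-values. Keep the univariate regressions as description only.
- **Report** crude and adjusted estimates side by side with 95% confidence intervals.

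The cost is a sentence or two of text and a few degrees of freedom. With four regions as an illustration, that is 1 (serostatus) + 6 (smoking, alcohol, parity, height, weight, diabetes, one each) + 3 = 10 for 200 pairs. The simulated standard error is typically 0.19-0.20 SD rather than 0.18-0.19 SD. If all confounders exaggerate the effect, the full model gives up a little power (71% v 74%).

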A prospectively ascertained cross-sectional study using mother-child data pairs will be conducted in pregnant migrants attending for medical care in Rome, Dublin and Jena from *Schistosoma*-endemic areas.

Inclusion criteria: Pregnant women >18 years originally from endemic countries and areas (as defined by WHO) who give written informed consent to the study.

Exclusion criteria: Placental pathology due to any cause and any other medical condition affecting fetal growth.

Primary analysis: Association between *Schistosoma* seropositivity and birth weight (details below).

Secondary analyses: Association between *Schistosoma* seropositivity and intrauterine growth restriction (IUGR)¹⁶ (defined as birth weight below the 10th birth weight percentile), stillbirth and premature delivery.

Assessments: A questionnaire (see below) will be completed on each subject including demographics, age, medical history, and history of *Schistosoma* infection. Data concerning the primary (birth weight percentiles) and secondary outcomes (intrauterine growth restriction, stillbirth and premature delivery) will be collected. The necessary values consist of gestational age, weight and sex of the new born. Gestational age will be either determined by ultrasound or by calculation of the last menstrual period. *Schistosoma*-specific antibody detection will be performed locally on serum by a commercially available *in vitro* diagnostics certified qualitative ELISA test.

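### IUGR and premature delivery get only unadjusted Fisher tests, so a reported association with serostatus could reflect origin, smoking or parity

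*Combined protocol and SAP*

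**What the plan says.** The Methodology section describes an observational design: "A prospectively ascertained cross-sectional study using mother-child data pairs will be conducted in pregnant migrants". Groups are formed by serology, and "we expect 20% of the serologic tested samples to be positive", that is, about 40 against 160 pairs.

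The Questionnaires paragraph lists the influences on the outcome: "Known categorical variables that are affecting fetal growth are smoking, alcohol, diabetes, baby gender, ethnic origin and parity". It says that country of origin will make ethnic origin more precise. It also lists influences on the serological result, among them freshwater contact in the area of origin or on the journey, and time since migration.

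The Statistical analysis section treats the outcomes differently:

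- **Birth weight percentile:** a Mann-Whitney-Wilcoxon test, then univariate regressions, then multiple linear regression with confounders retained at p<0.2.
- **IUGR, stillbirth, premature delivery:** an exploratory comparison "using Fishers exact tests for the dichotomous variables (IUGR, stillbirth and premature delivery"), with effect sizes and 95% confidence intervals. No logistic, stratified or other adjusted analysis is given for any binary outcome.

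**The concern.** By the plan's own account, origin bears on both exposure (through freshwater contact) and outcome (through ethnic origin). Smoking and parity may also differ between the serogroups. The plan accepts that the percentile needs adjustment, and gives no reason for omitting it for IUGR and premature delivery.

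The Project Objectives name premature delivery and stillbirth alongside birth weight. The crude estimates and intervals would be the only direct answer reported for IUGR and premature delivery, and they could show an association where serostatus has no effect, or hide one that exists.

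**Working it through.** **1. The plan's own figure.** The Sample size estimates paragraph says that the study "has a power of 80% to detect a standardized mean difference in birth weight percentiles of 0.5", with "planning by Student's test for 4:1 sample size ratio; nQuery 3.0". With 40 v 160 and a difference of 0.5 SD, the noncentrality is 0.5 / √(1/40 + 1/160) = 2.83. The two-sided 5% t test then has power 80.4% (80.7% by normal approximation), so the stated figure reproduces. It covers the primary comparison only.

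**2. Expected IUGR events.** The plan gives a rate of 5-10% of pregnancies.

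- All pairs: 200 × 0.05 = 10 to 200 × 0.10 = 20.
- Seropositive, if there is no effect: 40 × 0.05 = 2 to 40 × 0.10 = 4.
- Seronegative: 160 × 0.05 = 8 to 160 × 0.10 = 16.

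No rate is given for premature delivery or stillbirth, so their event counts cannot be computed.

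**3. Spurious association with no true effect.** The documents give no confounder strength or imbalance, so every value in this step is assumed. Let a share p of a serogroup come from a higher-risk region with IUGR risk rH, and the rest from a region with risk rL. The crude risk in that serogroup is p × rH + (1 − p) × rL. The rejection rate is the sum of the binomial probabilities of all 40 v 160 tables whose two-sided Fisher p-value is at most 0.05.

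| Share in higher-risk region (pos v neg) | Regional risks | Crude risks (pos v neg) | RR | Fisher rejection |
|---|---|---|---|---|
| 60% v 40% | 10%, 6% | 8.4% v 7.6% | 1.11 | 4.3% |
| 70% v 40% | 15%, 7% | 12.6% v 10.2% | 1.24 | 6.3% |
| 80% v 30% | 8%, 3% | 7.0% v 4.5% | 1.56 | 9.4% |
| 80% v 30% | 16%, 6% | 14.0% v 9.0% | 1.56 | 14.3% |

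Example, last row: 0.8 × 16% + 0.2 × 6% = 14%; 0.3 × 16% + 0.7 × 6% = 9%; 14/9 = 1.56.

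Without confounding, Fisher's test rejects in 2.6% of studies at a 5% rate and 3.4% at a 10% rate.

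A second set of assumptions gives a similar range. It uses a confounder odds ratio of 2 to 3, prevalences of 40% v 20%, 60% v 20% or 70% v 30%, and a 5-10% risk without the confounder. Crude odds ratios are 1.16 to 1.57 and rejection is 4.5% to 14.5%.

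**4. Does a small adjusted model work with so few events?** Studies were simulated under the two 80% v 30% scenarios (about 20 and 10 events), with Firth-penalised logistic regression on serostatus including region. The median odds ratio falls from about 1.7 crude to between about 1.0 and 1.1 adjusted at both event counts. The standard error is about 4% to 8% larger.

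**5. How many covariates?** Serostatus, three centres (two parameters), smoking and parity make five parameters: 10/5 = 2 to 20/5 = 4 events per parameter. Serostatus with one single-parameter covariate has 10/2 = 5 to 20/2 = 10; with two, 10/3 = 3.3 to 20/3 = 6.7. Only the short model is defensible.

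**The case against.** **IUGR is not wholly uncontrolled.** A reader might infer that no confounder is handled in any form. That goes too far. Percentiles use gestational age and sex. The exclusion criteria remove placental pathology and other medical conditions affecting growth, and entry is restricted to women from endemic areas. IUGR is also a cut of the primary variable, for which adjusted regression is planned. All this stands, but a shift in the mean percentile is not an adjusted IUGR odds ratio. Origin within endemic areas, smoking and parity remain open, and premature delivery gets nothing from the percentile model.

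**The tests are exploratory.** A reader might also infer that any difference would be taken as an effect of schistosomiasis. The Purpose and the secondary analyses speak of association, so the documents support only that it could be, given that the aim speaks of impact. The exploratory label tempers significance claims; it does not remove bias from the reported estimates.

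**The plan compares the secondary analyses to the sensitivity analyses.** This might be taken to extend regression to the binary outcomes. The sentence names only Fisher tests, so the natural reading is that it refers to exploratory status.

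**The plan says IUGR can be compared across multi-ethnic populations.** If so, the regional risk differences assumed here are too large. That is a fair limit on the magnitude, but it does not address smoking or parity, or premature delivery.

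**The covariates listed concern fetal growth.** They are not shown to be the right ones for premature delivery. That stands, and the choice for that outcome needs its own justification.

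**Conclusion.** The point holds as a cheap improvement to secondary analyses. IUGR and premature delivery have only crude comparisons in an observational study that collects the likely confounders. The gap is complete for premature delivery and partial for IUGR.

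With no true effect, the illustrations give a crude IUGR risk ratio of about 1.1 to 1.6 and Fisher rejection of about 4% to 14%, against about 3% without confounding. These figures show what confounding could do and do not estimate what it will do. The upper end needs an 80% v 30% imbalance and a 2.7-fold regional risk (16/6), or similarly strong values, and the mildest case stays below the nominal 5%. No magnitude can be given for premature delivery.

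It would be tempting to conclude that the full list of collected factors should be adjusted for. The 10 to 20 IUGR events implied by the plan do not support that. The primary analysis is not affected by this point.

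**What to change.** - Keep Fisher's exact test as the crude comparison.
- For premature delivery and IUGR, add a Firth-penalised logistic regression on serostatus with one or two covariates fixed before the data are seen, not chosen by the p<0.2 screen. Take region of origin first, coded in few categories, then smoking or parity if events allow. State the rule for adding the second covariate, and justify the choice separately for premature delivery.
- Report the adjusted odds ratio and 95% confidence interval beside the crude result.
- Report stillbirth as counts with exact intervals only.

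The cost is SAP wording and two models on data already collected. The intervals become slightly wider (standard errors about 4% to 8% larger in the simulated scenarios). There is room for only one or two covariates, so residual confounding should be acknowledged in the report.
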